14.2. REGULATORY APPROVAL / NOTIFICATION

This clinical study protocol, title, and a list of investigational sites, IEC approvals, as well as other relevant documentation will be submitted to the local Regulatory Authorities for review and approval prior to study start. Upon completion, the Regulatory Authorities will be notified the study has ended. The study will only be undertaken in compliance with the local regulatory requirements.

14.3. ICH GCP

This study will be conducted in accordance with the current ICH-GCP Guideline E6. GCP is an international ethical and scientific quality standard for designing, conducting, recording and reporting studies that involve the participation of human subjects. Compliance with this standard provides public assurance that the rights, safety and well-being of study subjects are protected, consistent with the principles that have their origin in the Declaration of Helsinki, and that the clinical study data are credible.

14.4. INFORMED CONSENT

The investigator or designated personnel must explain the study and the implications of participation (e.g., objectives, methods, anticipated benefits and possible risks) to potential subjects or their legally acceptable representatives prior to any study-related activity. Subjects will be informed that their participation is voluntary and that they may withdraw from the study at any time. They will be informed that choosing not to participate or to withdraw from the study will not have an impact on the care the subject will receive for the treatment of his/her disease. In case the subject is unable to read and write, an impartial witness must confirm the informed consent.

The subject will be given sufficient time to read the ICF and to ask additional questions. After this explanation and before entry in the study, consent should be appropriately recorded by means of the subject's personally dated signature or by the signature of an independent witness who certifies the subject's consent in writing. After having obtained the consent, a copy of the signed and dated informed consent must be given to the subject.

If new information becomes available that may be relevant to the subject's willingness to participate in the study, the subject will be informed in a timely manner by means of an updated informed consent form. This amended informed consent form will be signed and dated by the subject and the investigator to document the willingness of the subject to continue with the study.

This signed and dated amended version will be filed together with the initial signed and dated informed consent form.

15. FINANCING AND INSURANCE

15.1. FINANCIAL DISCLOSURE

The disclosed financial interest of the investigator must be collected before screening of the first subject, following study completion at the investigator site and one year following overall study completion. The investigator should promptly update this information if any relevant changes occur during this period. Disclosable financial interests will be recorded on the Investigator Financial Disclosure Form.

Any investigator(s) added as investigational staff must complete the Investigator Financial Disclosure Form at the beginning of their participation in the study. For any investigator(s) leaving the site prior to study completion, an Investigator Financial Disclosure Form should be obtained at the end of their contribution to the study.

15.2. INDEMNIFICATION

The sponsor will indemnify the investigator and hold harmless the investigator and his or her medical staff from any claim for damages, demand or cost arising from the activities to be carried out in compliance with the clinical study protocol.

The investigator must notify the sponsor immediately upon notice of any claims or lawsuits.

15.3. INSURANCE

The sponsor ensures that suitable clinical study insurance coverage is in place prior to the start of clinical study. For subjects treated according to the clinical study protocol, injury possibly arising from participating in this study is covered by the liability insurance of the sponsor, unless malpractice from the investigator.

16. DATA QUALITY CONTROL / ASSURANCE

16.1. MONITORING

This clinical study will be monitored by sponsor representatives according to the current Standard Operating Procedure for the monitoring of clinical studies.

The monitor will perform on-site monitoring visits as frequently as necessary which will be documented on the monitoring log. Shortly before the study starts, the monitor will meet with the investigator and study staff involved to review the study-specific procedures on study conduct and recording the data in the eCRF. The first monitoring visit will take place as soon

as possible after first enrollment at the site and the investigator shall permit the monitor to verify the progress of the study on a continues basis. The investigator shall make the eCRFs available, provide missing or corrected data and sign the eCRFs. Key data transcribed onto the eCRFs, such as the subject's sex, date of birth, assessment dates, test results etc., will be reviewed against the available source documents. Personal information will be treated as strictly confidential and will not be made publicly available. Any inconsistency between source data and data recorded in the eCRF will be corrected.

The sponsor will ensure that appropriate QC steps are included into the different clinical study processes to guarantee adequate protection of the subjects and to guarantee the quality of the data.

Appendix 2 HRCT/Biopsy Central Review Criteria

All chest HRCTs and histopathology slides of surgical lung biopsies (if available) will be centrally reviewed by an independent radiologist and an independent histopathologist in order to confirm the diagnosis of IPF.

Confirmed IPF Diagnosis Based on HRCT only (No Lung Biopsy Available)

In the absence of a surgical lung biopsy, HRCT must qualify as “consistent with IPF”. This will be defined as meeting either criteria A, B and C, or criteria A and C, or criteria B and C provided below.

- A) Definite honeycomb lung destruction with basal and peripheral predominance.
- B) Presence of reticular abnormality AND traction bronchiectasis consistent with fibrosis with basal and peripheral predominance.
- C) Atypical features are ABSENT, specifically: nodules and consolidation. Ground glass opacity, if present, is less extensive than reticular opacity pattern.

Appearances of a fibrosing lung disease with no definite HRCT features of a specific etiology will be considered “possible IPF”. Convincing HRCT appearances of a diffuse lung disease other than IPF will be considered “definitely not IPF”. Subjects with “possible IPF” (unless clear IPF diagnosis based on the SLB data) and “definitely not IPF” will not be allowed for inclusion in the study.

Confirmed IPF Diagnosis Based on Both HRCT and Lung Biopsy

In the presence of a surgical lung biopsy, the histology will be reviewed, based on the most recent ATS/ERS/JRS/ALAT Guideline. In such case, there will be a multi-disciplinary team approach to confirm or exclude the diagnosis of IPF. An HRCT “possible IPF” coupled with a surgical biopsy of “definite IPF” or “probable IPF”, upon multidisciplinary team discussion, could qualify for inclusion as “consistent with IPF”.

The decision-schedule used to decide whether a subject is eligible for study entry is provided below.

	SLB: Definite IPF	SLB: Probable IPF	SLB: Possible IPF	SLB: Non Classifiable IPF
HRCT: Consistent with IPF	Eligible	Eligible	Eligible	Eligible
HRCT: Possible IPF	Eligible	Eligible	Not Eligible	Not Eligible
HRCT: Definitely not IPF	Not Eligible	Not Eligible	Not Eligible	Not Eligible

HRCT=high-resolution computed tomography; IPF=idiopathic pulmonary fibrosis; SLB=surgical lung biopsy

An overview of the histopathological criteria for definite-probable-possible-non classifiable IPF is provided below.

SLB: Definite IPF (all 4 criteria met)	SLB: Probable IPF	SLB: Possible IPF (all 3 criteria met)	SLB: Non Classifiable IPF (any of the 6 criteria)

 – Evidence of marked fibrosis/ architectural distortion, ± honeycombing in a predominantly subpleural/ paraseptal distribution – Presence of patchy involvement of lung parenchyma by fibrosis – Presence of fibroblast foci – Absence of features against a diagnosis of IPF suggesting an alternate diagnosis (see fourth column) 	
 – Evidence of marked fibrosis / architectural distortion, ± honeycombing – Absence of either patchy involvement or fibroblastic foci, but not both – Absence of features against a diagnosis of IPF suggesting an alternate diagnosis (see fourth column) – OR – Honeycomb changes only 	
 – Patchy or diffuse involvement of lung parenchyma by fibrosis, with or without interstitial inflammation – Absence of other criteria for IPF (see IPF PATTERN column) – Absence of features against a diagnosis of IPF suggesting an alternate diagnosis (see fourth column) 	
 – Hyaline membranes – Organizing pneumonia – Granulomas – Marked interstitial inflammatory cell infiltrate away from honeycombing – Predominant airway centered changes – Other features suggestive of an alternate diagnosis

IPF=idiopathic pulmonary fibrosis; SLB=surgical lung biopsy

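### Appendix 2 marks one biopsy category Eligible although its own histology table defines that category by features against IPF

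*Protocol*

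**What the plan says.** Inclusion criterion 4 (Protocol section 4.2.2) requires IPF to be diagnosed by a multidisciplinary team and confirmed by central review of the HRCT and, where there is one, the surgical lung biopsy (SLB). It refers to Appendix 2 for the details. Section 4.1 likewise makes SLB review part of confirming the diagnosis, and section 4.2.1 describes the roughly 24 subjects as having centrally confirmed IPF.

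Appendix 2 then treats two situations:

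- **No biopsy.** The HRCT has to carry the diagnosis alone: "In the absence of a surgical lung biopsy, HRCT must qualify as" consistent with IPF.
- **Biopsy available.** Under the heading "Confirmed IPF Diagnosis Based on Both HRCT and Lung Biopsy", the appendix says that "there will be a multi-disciplinary team approach to confirm or exclude the diagnosis of IPF". It adds that a possible-IPF HRCT with a definite or probable biopsy, "upon multidisciplinary team discussion, could qualify for inclusion as" consistent with IPF.

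A three-by-four table follows, introduced by "The decision-schedule used to decide whether a subject is eligible for study entry is provided below". In its row "HRCT: Consistent with IPF", all four biopsy categories read Eligible.

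The histology table defines the four categories. Definite, Probable and Possible each list as a criterion "Absence of features against a diagnosis of IPF suggesting an alternate diagnosis (see fourth column". The fourth column, Non Classifiable IPF, is met by any one of six items: hyaline membranes, organizing pneumonia, granulomas, marked inflammatory infiltrate away from honeycombing, predominantly airway-centered change, or anything else suggesting another diagnosis.

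**The concern.** The two tables do not agree about the fourth biopsy category. One treats its contents as evidence against IPF; the other admits subjects who have those contents, provided the HRCT is consistent with IPF. A biopsy step meant to confirm or exclude the diagnosis then has no power to exclude in that row, and criterion 4, which counts the biopsy as part of the confirmation, is not met in any plain sense.

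At stake is who is in the trial population. If the table is followed as the entry rule it claims to be, a subject with adverse histology can be recorded as centrally confirmed. In a study of about 24 subjects, even one such subject is a visible share of an arm.

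**Working it through.** No sample size, power or error-rate figure is involved, so the check is a cross-reading of the two Appendix 2 tables, with a count.

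**Step 1. Eligibility table.** 3 HRCT rows × 4 SLB columns = 12 cells.

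| HRCT | Definite | Probable | Possible | Non Classifiable |
|---|---|---|---|---|
| Consistent with IPF | Eligible | Eligible | Eligible | **Eligible** |
| Possible IPF | Eligible | Eligible | Not | Not |
| Definitely not IPF | Not | Not | Not | Not |

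Eligible by row: 4 + 2 + 0 = 6.

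**Step 2. What each category says about the six fourth-column features.**

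| SLB category | Position on the six features | Eligible cells |
|---|---|---|
| Definite | absence listed as a criterion | 2 |
| Probable | absence listed as a criterion (an alternative route, honeycomb changes only, does not repeat it) | 2 |
| Possible | absence listed as a criterion | 1 |
| Non Classifiable | presence of at least one required | 1 |

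Check: 2 + 2 + 1 = 5 Eligible cells in categories that list absence, plus 1 in a category that requires presence; 5 + 1 = 6. The disputed entry is the only Eligible cell of its kind.

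**Step 3. Could it be a damaged table?** A shifted column would not alter the entry, because all four cells in that row read Eligible. The amendment's summary of changes does not touch Appendix 2.

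**Step 4. Does any other text resolve it?**

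- The prose lets a consistent HRCT stand alone only where there is no biopsy. No sentence says that it outweighs an adverse one.
- The multidisciplinary step applies to every biopsy case. For a possible-IPF HRCT with a definite or probable biopsy, the prose is conditional on team discussion while the table simply reads Eligible. Eligible may therefore mean subject to the team's decision, but the appendix does not say so.
- HRCT criterion C ("Atypical features are ABSENT, specifically: nodules and consolidation") concerns imaging. Exclusion 8 reaches ILD associated with known primary diseases, exposures or drugs. Exclusion 11 is investigator judgement. Each may stop some such subjects; none excludes on the listed histology.

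**Step 5. Scale, for illustration only.** About 24 subjects at 3:1 gives 24 × 3/4 = 18 active and 24 × 1/4 = 6 placebo. One subject admitted through this cell would be 1/24 = 4.2% of the trial, 1/18 = 5.6% of the active arm or 1/6 = 16.7% of the placebo arm. The Protocol does not give the number of subjects with a biopsy, so how many would enter this way cannot be calculated.

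**The case against.** The best defence is that the table applies an HRCT-led rule. Appendix 2 bars subjects with a definitely-not-IPF HRCT, and those with a possible-IPF HRCT unless the biopsy gives a clear diagnosis. The biopsy appears there only as a rescue for the possible-IPF group, and the three rows of the table follow that pattern. On this view, a consistent HRCT is meant to prevail over a biopsy that could not be classified. This does not settle the matter. The sentence stands under the HRCT-only heading and says which HRCT categories are barred, not that a consistent HRCT outweighs an adverse biopsy. The label Non Classifiable might suit an uninformative sample, but the column's content consists of positive features that the same table calls adverse.

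A second argument is that, if criterion 4 demands confirmation from the biopsy itself, the consistent-HRCT and Possible-biopsy cell is equally suspect. The two cells differ: Possible requires the adverse features to be absent, so it is weak evidence rather than contrary evidence.

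A third argument is that the table is not the only gate. This stands in part. A subject whose team concludes that the disease is not IPF should fail criterion 4 whatever the cell says, and the other gates may catch more. It limits the likely consequences without making the two tables agree.

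Finally, the appendix says histology is reviewed against a professional guideline and calls its table an overview. How that guideline handles discordant HRCT and histology cannot be checked from the Protocol, which is one reason to leave the choice of rule to the diagnostic experts.

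**Conclusion.** The concern holds. Appendix 2 contradicts itself in one cell, and that cell does not fit inclusion criterion 4 or the stated purpose of the biopsy review. Confidence is high that the wording is unreconciled. The Protocol does not show whether the cell, the column heading or the column content is at fault, and no view on the right diagnostic rule is offered here.

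The conclusion assumes that the table is applied as introduced, namely as what decides entry. Admission of a subject without IPF is possible but not shown. No stated power or error rate is affected, because section 6.1 says the sample size was not set on strict statistical criteria. The point should be fixed because it concerns a stated entry rule in a small trial and costs little to correct.

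A separate, minor slip: the third histology column refers the reader to an IPF pattern column, and no column carries that name.

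**What to change.** By amendment to Appendix 2:

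1. Have the sponsor's diagnostic experts reconcile the disputed cell, the heading and content of the fourth histology column, and inclusion criterion 4. One way is to separate histology that truly cannot be classified from histology suggesting another diagnosis, and to assign eligibility to each.
2. Add one sentence stating whether Eligible in the table is final or subject to the multidisciplinary decision. This also settles the mismatch between prose and table for possible-IPF HRCTs.
3. Correct the reference to the non-existent column.

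The cost is one cell or one column, one sentence and one cross-reference. Sample size, visits and analyses do not change. The effect on the number of eligible subjects depends on which element the experts find at fault and cannot be given from the Protocol.

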Appendix 3 DLCO

At visit 1, DLCO must meet the following criteria (Macintyre, et al., 2005):

- 30% predicted of normal \leq DLCO corrected for hemoglobin

For predicted normal values, different sites may use different prediction formulas, based on the method used to measure DLCO. In any case, the method used must be in compliance with the ATS/ERS guideline on DLCO measurements (Macintyre, et al., 2005), and the prediction formula appropriate for that method.

Raw data (gas mixture, equation used for prediction of normal) must be captured.

DLCO corrected for hemoglobin:

- Males: DLCO corrected for hemoglobin = DLCO measured \times (10.22+Hb) / 1.7Hb
- Females: DLCO corrected for hemoglobin = DLCO measured \times (9.38+Hb) / 1.7Hb

Hemoglobin is expressed in g/dL.

Appendix 4 CYP3A4 Inducers

The following drugs/nutraceuticals are known CYP3A4 inducers (non-exhaustive list):

- Carbamazepine
- Phenytoin
- Oxcarbazepine
- Phenobarbital
- Butalbital
- St. John's wort
- Rifampicin
- Rifabutin
- Pioglitazone
- Troglitazone
- Glucocorticoids

1. RATIONALE

The description for storage and use of left over BALF samples was missing while the purpose of these samples is fully explained in the PIS/ICF. The protocol is updated to align both documents, to correct typo's and to record the change of Medical Monitor and Medical Lead responsibility. These updates are considered **non-substantial**.

2. SUMMARY OF CHANGES FROM PREVIOUS VERSION

Section	Summary of Changes
Cover page	Update Medical Lead
Emergency Contact information	Update Medical Monitor
4.1	Correct typo in section 4.1: Week 98 [Day 98] should be Week 14 [Day 98].
5.4.5	Correct typo for reference to Appendix 4, should be Appendix 5
5.8	Text corrected to align with the approved PIS/ICF

4. CHANGES IN CLINICAL STUDY SPECIFIC PROCEDURES

Change in section 4.1. Overall Study Design

...

The subjects will visit the clinical study center at screening (Day-28 to Day -4), Day -1 (baseline), Week 1 (Day 7), Week 2 (Day 14), Week 4 (Day 28), Week 8 (Day 56), and Week 12 (Day 84) or the early discontinuation visit (EDV). In addition, a follow-up visit will be planned 2 weeks after the last administration of study drug (~~Week 98~~ **Week 14** [Day 98]). Each subject will be in the study for up to approximately 18 weeks (from screening to follow-up). The end of the study (EOS) will be defined as the last contact with the last subject in the study.

Change in section 5.4.5 Electrocardiogram

A 12-lead ECG will be performed predose at the time points indicated in the study flow chart (provided in Section 1) and according to sequence of study assessments as described in Section 5.1. The ECG must be taken after 5 min in the supine position, prior to any blood sampling. Each ECG will be interpreted by the investigator for clinical significance.

Normal ranges are provided in ~~Appendix 4~~ **Appendix 5**

Change in section 5.8. Total Blood Volume

...

After the study is completed, any left-over blood samples **and bronchoalveolar lavage samples** may be stored under the control of the sponsor. These samples may be used by the sponsor/partner, or by other companies belonging to the sponsor for future research on the mode of action of GLPG1690 and/or future research in IPF.

SIGNATURE PAGE – SPONSOR

Title Randomized, Double-Blind, Parallel Group, Placebo-Controlled, Multicenter, Exploratory Phase IIa Study to Assess Safety, Tolerability, Pharmacokinetic and Pharmacodynamic Properties of GLPG1690 Administered for 12 Weeks in Subjects with Idiopathic Pulmonary Fibrosis (IPF)

This Clinical Study Protocol Amendment has been reviewed and approved by the sponsor to ensure compliance with International Conference on Harmonization (ICH) guidelines for Good Clinical Practices (GCP) and applicable regulatory requirements.

Medical Lead

Signature

Date

SIGNATURE PAGE – INVESTIGATOR

Title Randomized, Double-Blind, Parallel Group, Placebo-Controlled, Multicenter, Exploratory Phase IIa Study to Assess Safety, Tolerability, Pharmacokinetic and Pharmacodynamic Properties of GLPG1690 Administered for 12 Weeks in Subjects with Idiopathic Pulmonary Fibrosis (IPF)

